3.2.6 Pharmaceutical Data - Tremelimumab

Supplied:

Supplied as a vialed solution containing 400 mg (nominal) tremelimumab. The solution contains 20 mg/mL tremelimumab, 20 mM histidine/histidine-HCI, 222 mM trehalose dihydrate, 0.02% (w/v) polysorbate 80, 0.27 mM disodium edetate dehydrate (EDTA), pH 5.5.

Storage:

Tremelimumab must be stored at 2°C to 8°C and must not be frozen. The product should be protected from light when not in use.

Route of Administration: Intravenous.

Please refer to the IND.228 Pharmacy Manual for additional details.

3.3 Fixed Dosing in Durvalumab and Tremelimumab

A population PK model was developed for durvalumab using monotherapy data from a phase I study (study 1108; N=292; doses= 0.1 to 10 mg/kg Q2W or 15 mg/kg Q3W; solid tumours). Population PK analysis indicated only minor impact of body weight (WT) on PK of durvalumab (coefficient of ≤ 0.5). The impact of body WT-based (10 mg/kg Q2W) and fixed dosing (750 mg Q2W) of durvalumab was evaluated by comparing predicted steady state PK concentrations (5th, median and 95th percentiles) using the population PK model. A fixed dose of 750 mg was selected to approximate 10 mg/kg (based on median body WT of ~75 kg). A total of 1000 patients were simulated using body WT distribution of 40–120 kg. Simulation results demonstrate that body WT-based and fixed dosing regimens yield similar median steady state PK concentrations with slightly less overall between-subject variability with fixed dosing regimen.

Similarly, a population PK model was developed for tremelimumab using data from Phase 1 through Phase 3 (N=654; doses= 0.01 to 15 mg/kg Q4W or Q90D; metastatic melanoma) [Wang 2014]. Population PK model indicated minor impact of body WT on PK of tremelimumab (coefficient of ≤ 0.5). The WT-based (1 mg/kg Q4W) and fixed dosing (75 mg/kg Q4W; based on median body WT of ~75 kg) regimens were compared using predicted PK concentrations (5th, median and 95th percentiles) using population PK model in a simulated population of 1000 patients with body weight distribution of 40 to 120 kg. Similar to durvalumab, simulations indicated that both body WT-based and fixed dosing regimens of tremelimumab yield similar median steady state PK concentrations with slightly less between-subject variability with fixed dosing regimen.

Similar findings have been reported by others [*Ng 2006, Wang 2009, Zhang 2012, Narwal 2013*]. Wang and colleagues investigated 12 monoclonal antibodies and found that fixed and body size-based dosing perform similarly, with fixed dosing being better for 7 of 12 antibodies. In addition, they investigated 18 therapeutic proteins and peptides and showed that fixed dosing performed better for 12 of 18 in terms of reducing the between-subject variability in pharmacokinetic / pharmacodynamics parameters [*Zhang 2012*].

A fixed dosing approach is preferred by the prescribing community due to ease of use and reduced dosing errors. Based on average body WT of 75 kg, a fixed dose of 1500mg Q4W and 75 mg tremelimumab (equivalent to 1 mg/kg) is planned.

Fixed dosing of durvalumab and tremelimumab is recommended only for subjects with > 30 kg body weight due to endotoxin exposure. Patients with a body weight less than or equal to 30 kg should be dosed using a weight-based dosing schedule.

4.0 STUDY POPULATION

The trial population will consist of patients with advanced (metastatic or locally advanced) histologically confirmed rare cancers as defined in section 4.1.1 that is unresectable and for which no curable therapy exist.

This study is designed to include women and minorities as appropriate, but is not designed to measure differences in intervention effects in these patient populations.

4.1 Eligibility Criteria

There will be NO EXCEPTIONS to eligibility requirements at the time of registration. Questions about eligibility criteria should be addressed prior to registration.

The eligibility criteria for this study have been carefully considered. Eligibility criteria are standards used to ensure that patients who enter this study are medically appropriate candidates for this therapy. For the safety of the patients, as well as to ensure that the results of this study can be useful for making treatment decisions regarding other patients with similar diseases, it is important that no exceptions be made to these criteria for admission to the study.

Patients must fulfill all of the following criteria to be eligible for admission to the study:

- 4.1.1 Patients must have histologically and/or cytologically confirmed cancer that is advanced / metastatic / recurrent or unresectable and for which no curative therapy exists as follows:
 - 1. Salivary carcinoma (excluding adenoid cystic carcinoma histology)
 - 2. Carcinoma of unknown primary with tumour infiltrating lymphocytes (TILs) and/or expressing PD-L1
 - 3. Mucosal melanoma
 - 4. Acral melanoma
 - 5. Osteosarcoma
 - 6. Undifferentiated pleomorphic sarcoma
 - 7. Clear cell carcinoma of the ovary
 - 8. Squamous cell carcinoma of the anal canal (SCCA)
- 4.1.2 All patients must have a tumour tissue from their primary or metastatic tumour available (See Section 11.2 for slide specifications, as well as section 12.1).
- 4.1.3 Presence of clinically and/or radiologically documented disease. All radiology studies must be performed within 28 days prior to registration (within 35 days if negative).

All patients must have at least one measurable lesion as defined by RECIST 1.1 that has not been the site of the protocol mandated biopsy. The criteria for defining measurable disease are as follows:

CT scan (with slice thickness of 5 mm)	$\geq 10 \text{ mm}$	\rightarrow	longest diameter
Lymph nodes by CT scan	\geq 15 mm	\rightarrow	measured in short axis

- 4.1.4 Patients must be ≥ 16 years of age.
- 4.1.5 Patients must have an ECOG performance status of 0 or 1.

4.1.6 Previous Therapy

Cytotoxic Chemotherapy:

Patients may have received prior chemotherapy – no limit on number of prior regimens.

Other Systemic Therapy:

Patients may have received other prior therapies including, angiogenesis inhibitors, PARP inhibitors or signal transduction inhibitors (tyrosine kinase inhibitors). Prior therapy with PD-1/PD-L1 or CTLA-4 inhibitors is not allowed.

Patients must have recovered from all reversible toxicity related to prior chemotherapy or systemic therapy (unless grade 1, irreversible, or considered by investigator as not clinically significant) and have adequate washout as follows:

Longest of one of the following:

- Two weeks
- 5 half-lives for investigational agents
- Standard cycle length of standard therapies

Radiation:

Prior external beam radiation is permitted provided a minimum of 28 days (4 weeks) have elapsed between the last dose of radiation and date of registration. Exceptions may be made for low-dose, non-myelosuppressive radiotherapy after consultation with CCTG senior investigator. Concurrent radiotherapy is not permitted. Patients planned for concurrent chemotherapy-radiation are not eligible.

Surgery:

Previous surgery is permitted provided that a minimum of 28 days (4 weeks) have elapsed between any major surgery and date of registration, and that wound healing has occurred.

4.1.7 *Laboratory Requirements*

(must be done within 7 days prior to registration)

	Absolute neutrophils	$\geq 1.5 \text{ x } 10^9/\text{L}$			
Hematology	Platelets	$\geq 100 \text{ x } 10^9/\text{L}$			
	Hemoglobin	\geq 90 g/L			
	Bilirubin	\leq 1.5 x ULN (upper limit of normal)*			
	AST and ALT	\leq 2.5 x ULN (if liver metastases are present, \leq 5 x ULN)			
Chemistry	Serum creatinine	< 1.25 x ULN			
	or:				
	Creatinine clearance**	\geq 40 mLs/min			
 * If confirmed Gilbert's, eligible providing ≤ 3 x ULN. ** Creatinine clearance to be measured directly by 24 hour urine sampling or as calculated by Cockcroft and Gault equation below: 					
Females: $GFR = \frac{1.04 \text{ x} (140\text{-age}) \text{ x weight in } \text{kg}}{\text{serum creatinine in } \mu\text{mol/L}}$					
Males: G	Males: GFR = $\frac{1.23 \text{ x (140-age) x weight in kg}}{\text{serum creatinine in } \mu \text{mol}/\text{L}}$				

4.1.8 Patient consent must be appropriately obtained in accordance with applicable local and regulatory requirements. Each patient must sign a consent form prior to registration in the trial and prior to tests which are considered to be study specific (see Section 5.0) to document their willingness to participate.

Patients who cannot give informed consent (i.e. mentally incompetent patients, or those physically incapacitated such as comatose patients) are not to be recruited into the study. Patients competent but physically unable to sign the consent form may have the document signed by their nearest relative or legal guardian. Each patient will be provided with a full explanation of the study before consent is requested.

4.1.9 Women/men of childbearing potential must have agreed to use a highly effective contraceptive method. A woman is considered to be of "childbearing potential" if she has had menses at any time in the preceding 12 consecutive months. In addition to routine contraceptive methods, "effective contraception" also includes heterosexual celibacy and surgery intended to prevent pregnancy (or with a side-effect of pregnancy prevention) defined as a hysterectomy, bilateral oophorectomy or bilateral tubal ligation, or vasectomy/vasectomized partner. However, if at any point a previously celibate patient chooses to become heterosexually active during the time period for use of contraceptive measures outlined in the protocol, he/she is responsible for beginning contraceptive measures.

Female patients of childbearing potential who are sexually active with a non sterilized male partner must use at least one highly effective method of contraception while on study and for 6 months after the last dose of durvalumab and tremelimumab or for 3 months after the last dose of durvalumab alone. Male partners of a female subject and non-sterilized male patients who are sexually active with a female partner of childbearing potential must use male condom plus spermicide while on study and for 6 months after the last dose of durvalumab and tremelimumab or for 3 months after the last dose of durvalumab and tremelimumab or for 3 months after the last dose of durvalumab and tremelimumab or for 3 months after the last dose of durvalumab alone. Female partners of a male subject must use a highly effective method of contraception throughout this period. Cessation of birth control after this point should be discussed with a responsible physician. See Section 9.3.1 for additional details.

Women of childbearing potential will have a pregnancy test to determine eligibility as part of the Pre-Study Evaluation (see Section 5.0); this may include an ultrasound to rule-out pregnancy if a false-positive is suspected. For example, when beta-human chorionic gonadotropin is high and partner is vasectomized, it may be associated with tumour production of hCG, as seen with some cancers. Patient will be considered eligible if an ultrasound is negative for pregnancy.

Male patients should also refrain from donating sperm during the study and for 6 months after the last dose of durvalumab and tremelimumab or for 3 months after the last dose of durvalumab alone.

- 4.1.10 Patients must be accessible for treatment and follow-up. Patients registered on this trial must be treated and followed at the participating centre. This implies there must be reasonable geographical limits (for example: 1 ½ hour's driving distance) placed on patients being considered for this trial. (Call the CCTG office at [contact] if questions arise regarding the interpretation of this criterion.) Investigators must assure themselves the patients registered on this trial will be available for complete documentation of the treatment, response assessment, adverse events, and follow-up.
- 4.1.11 Subjects should not donate blood while participating in this study, or for at least 90 days following the last infusion of durvalumab or tremelimumab.
- 4.1.12 In accordance with CCTG policy, protocol treatment is to begin within 2 working days of patient registration.
- 4.2 Ineligibility Criteria

Patients who fulfill any of the following criteria are not eligible for admission to the study:

- 4.2.1 Patients with a history of other malignancies, except: adequately treated non-melanoma skin cancer, curatively treated in-situ cancer of the cervix, or other cancers curatively treated with no evidence of disease for \ge 5 years.
- 4.2.2 Active or prior documented autoimmune or inflammatory disorders including inflammatory bowel disease (e.g. colitis or Crohn's disease), diverticulitis with the exception of diverticulosis, celiac disease or other serious gastrointestinal chronic conditions associated with diarrhea), systemic lupus erythematosus, Sarcoidosis syndrome, or Wegener syndrome (granulomatosis with polyangiitis), rheumatoid arthritis, hypophysitis, uveitis, etc., within the past 3 years prior to the start of treatment. The following are exceptions to this criterion:
 - Patients with alopecia.
 - Patients with Grave's disease, vitiligo or psoriasis not requiring systemic treatment (within the last 2 years).

- Patients with hypothyroidism (e.g. following Hashimoto syndrome) stable on hormone replacement.
- 4.2.3 History of primary immunodeficiency, history of allogenic organ transplant that requires therapeutic immunosuppression and the use of immunosuppressive agents within 28 days of registration*
 - * NOTE: Intranasal/inhaled corticosteroids or systemic steroids that do not to exceed 10 mg/day of prednisone or equivalent dose of an alternative corticosteroid are permissible.
- 4.2.4 Live attenuated vaccination administered within 30 days prior to registration.
- 4.2.5 History of hypersensitivity to durvalumab or tremelimumab or any excipient. Any previous treatment with a PD1 or PD-L1 inhibitor, including durvalumab or an anti-CTLA4, including tremelimumab.
- 4.2.6 Patients who have experienced untreated and/or uncontrolled cardiovascular conditions and/or have symptomatic cardiac dysfunction (unstable angina, congestive heart failure, myocardial infarction within the previous year or cardiac ventricular arrhythmias requiring medication, history of 2nd or 3rd degree atrioventricular conduction defects). Patients with a significant cardiac history, even if controlled, should have a LVEF \geq 50%.
- 4.2.7 Untreated symptomatic brain metastases or brain metastases in whom radiation or surgery is indicated.
- 4.2.8 Concurrent treatment with other investigational drugs or anti-cancer therapy.
- 4.2.9 Patients with serious illnesses or medical conditions which would not permit the patient to be managed according to the protocol (including corticosteroid administration), or would put the patient at risk. This includes but is not limited to:
 - History of significant neurologic or psychiatric disorder which would impair the ability to obtain consent or limit compliance with study requirements.
 - Active infection requiring systemic therapy; (including any patient known to have active hepatitis B, hepatitis C or human immunodeficiency virus (HIV) or tuberculosis or any infection requiring systemic therapy).
 - Active peptic ulcer disease or gastritis.
 - Known pneumonitis or pulmonary fibrosis with clinically significant impairment of pulmonary function.
- 4.2.10 Pregnant or lactating women.

Men and women of child-bearing potential must agree to use adequate contraception as described in Section 4.1.9.

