7.0 TREATMENT PLAN

Although the Canadian Cancer Trials Group acts as the coordinating agency for the trial, the responsibility for treatment of patients rests with the individual investigator.

In accordance with CCTG policy, protocol treatment is to begin within 2 working days of patient registration.

7.1 Durvalumab and Tremelimumab Treatment Plan

7.1.1 Drug Administration

When durvalumab is given with tremelimumab, tremelimumab will be administered first. Durvalumab infusion will start approximately 1 hour after the end of tremelimumab infusion.

One cycle will be defined as 4 weeks. Tremelimumab will only be given for the first 4 cycles.

Agent(s)	Dose	Route	Duration	Schedule
Durvalumab	1500 mg	IV	60 min	Day 1 every 4 weeks
Tremelimumab	75 mg	IV	60 min	Day 1, cycles 1-4

Patients with a body weight of less than or equal to 30kg should be dosed using a weight based dosing schedule. See Section 3.3.

7.1.2 Premedication

No routine premedication (e.g. for nausea) or prophylaxis for hypersensitivity is required. Management of symptoms should take place as necessary (See Appendix II). Premedication is not expected to be required. See Appendix II with respect to premedication of patients that have had a prior \leq Grade 2 infusion-related reaction. Details of any premedication or concomitant medication given to manage or prevent adverse events should be recorded on the electronic case report form (eCRF).

7.1.3 *Patient Monitoring*

Patients will be monitored before, during infusion and after the infusion of tremelimumab and durvalumab with assessment of vital signs as specified in Section 5.0. A 1-hour observation period is recommended after the first infusion of durvalumab and tremelimumab. If no clinically significant infusion reactions are observed during or after the first cycle, subsequent infusion observation periods can be at the Investigator's discretion (suggested 30 minutes after each durvalumab and tremelimumab infusion).

Guidelines for management of infusion-related reaction are summarized in Appendix II.

All patients should be closely monitored according to guidelines in Section 5.0 and be advised to contact the treating centre in the case of significant toxicities.

7.1.4 *Dose Modifications*

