7.1.6 Management of Infusion Reactions

Guidelines for management of infusion-related reaction are summarized in Appendix II. The standard infusion times for both durvalumab and tremelimumab are 1 hour. However, if there are interruptions during infusion, the total allowed time should not exceed 8 hours at room temperature.

Study personnel must be trained to recognize and treat anaphylaxis. The study site must have immediate access to appropriate drugs and medical equipment to treat acute anaphylactic reactions, emergency resuscitation teams and equipment in addition to the ability to admit patients to an intensive care unit if necessary.

7.1.7 Dose Adjustments for Immune Related Adverse Events and Other (Non-Immune Related) Adverse Events Related to Study Therapy

Guidelines for dose modification and toxicity management of immune related and non-immune related adverse events are summarized in Appendix II.

Centres must contact CCTG in the event of severe event(s), especially when the use of drugs such as infliximab are considered.

7.2 Duration of Therapy

Treatment with durvalumab \pm tremelimumab (to a maximum of 4 doses, cycles 1-4) will continue until disease progression or unacceptable toxicity.

Exceptions to the duration of treatment for patients with continued response may be made after consultation with CCTG.

7.3 Patient Compliance

Treatment compliance will be monitored by drug accountability, as well as recording drug administration in the patient's medical record and case report form (CRF).

7.4 Concomitant Therapy

Details of any concomitant medications (prescription, non-prescription, or over-the-counter medications) taken by the patient at study entry and during protocol therapy must be recorded on the appropriate electronic case report forms (eCRFs).

7.4.1 Permitted

- Growth factors may be used according to centre policy to treat life threatening toxicity but cannot be used in place of protocol defined dose adjustments. Please consult CCTG senior investigator in the case of patients experiencing multiple delays as exceptions may be made for patients who are benefitting from protocol therapy.
- Other supportive and palliative care (e.g. pain control) as required throughout the study.
- Anti-emetics or anti-diarrheal agents as required.

7.4.2 Not Permitted

- Cytokines;
- Other anti-cancer treatment;
- Other investigational therapy;

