10.2 Duration of Protocol Treatment

(see Section 8.0 for response definition)

- For complete responders, therapy will continue until progression (refer to Section 7.2).
- For partial responders, therapy will continue until progression. For stable patients, therapy will continue until progression (refer to Section 7.2).
- Patients who progress (treatment failure) will stop all treatment and go off study at the time unequivocal progression is documented clinically and/or radiographically.

10.3 Therapy After Protocol Treatment is Stopped

At the discretion of the investigator.

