15.5 Retention of Patient Records and Study Files

All essential documents must be maintained as per C.05.012 and in accordance with ICH-GCP.

The Qualified Investigator must ensure compliance with the Regulations and the GCP Guideline from every person involved in the conduct of the clinical trial at the site.

Essential documents must be retained for 25 years following the completion of the trial at the centre (25 years post final analysis, last data collected, or closure notification to REB, whichever is later), or until notified by CCTG that documents no longer need to be retained.

In accordance with GCP 4.9.7, upon request by the monitor, auditor, REB or regulatory authority, the investigator/institution must make all required trial-related records available for direct access.

CCTG will inform the investigator/institution as to when the essential documents no longer need to be retained.

15.6 Centre Performance Monitoring

This study is eligible for inclusion in the Centre Performance Index (CPI).

Forms are to be submitted according to the schedule in the protocol. There are minimum standards for performance.

15.7 On-Site Monitoring/Auditing

CCTG site monitoring/auditing will be conducted at participating centres in the course of the study as part of the overall quality assurance program. The monitors/auditors will require access to patient medical records to verify the data, as well as essential documents, standard operating procedures (including electronic information), ethics and pharmacy documentation (if applicable).

As this trial is conducted under a CTA with Health Canada, your site may be subject to an inspection by the Health Canada Inspectorate.

The above mentioned documentation, in addition to any submitted source documents, may be accessed remotely in the event of a public health emergency either through remote access to Electronic Medical Records or through a secure file sharing portal.

The drug company, AstraZeneca, has reserved the right to audit CCTG activities. If AstraZeneca requests to audit participating centres they can only do so after consultation with CCTG and can only perform the audit as a co-audit with CCTG.

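### Section 4.1.9 does not say which contraception period governs a patient who has had both the combination and durvalumab alone; one reading ends up to 9 weeks early

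*Combined protocol and SAP*

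**What the plan says.** Section 4.1.9 sets the period for female patients of childbearing potential as the time on study and then "for 6 months after the last dose of durvalumab and tremelimumab or for 3 months after the last dose of durvalumab alone". The sentence on male patients and male partners uses the same two periods. Female partners follow the male rule: "Female partners of a male subject must use a highly effective method of contraception throughout this period". The sperm-donation sentence repeats it: "Male patients should also refrain from donating sperm during the study and for 6 months after the last dose of durvalumab and tremelimumab", followed by the same 3-month alternative for durvalumab alone.

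The treatment is sequential. Section 7.1.1 states: "One cycle will be defined as 4 weeks. Tremelimumab will only be given for the first 4 cycles". Section 7.2 caps tremelimumab and lets treatment run on: "to a maximum of 4 doses, cycles 1-4) will continue until disease progression or unacceptable toxicity".

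Section 9.3.1 refers back to section 4.1.9 for the contraceptive requirement and adds no duration. Section 9.3.2 sets 6 months after the last study treatment, but for reporting pregnancies, not for preventing them.

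Elsewhere the protocol does state precedence when several periods compete. The washout rule in section 4.1.6 says "Longest of one of the following", and section 15.5 on record retention says "25 years post final analysis, last data collected, or closure notification to REB, whichever is later".

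**The concern.** The wording would be clear if each patient received either the combination or durvalumab alone. Here the planned course is one and then the other, so anyone who continues past cycle 4 meets both descriptions. Section 4.1.9 gives no rule for that patient.

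Two readings are open. A site can run both clocks and stop at the later one. A site can also reason that the last drug given was durvalumab alone, so the 3-month period applies. The second reading can end contraception while the 6-month period after the last tremelimumab dose is still running.

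At stake is possible fetal exposure within a period the protocol itself treats as needing protection, and different advice from different sites for the same treatment history. The short reading also produces an anomaly: a patient given one extra durvalumab dose is protected for less time than a patient who stops after cycle 4.

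**Working it through.** The plan gives no figure for this gap, so there is none to reproduce. The check is date arithmetic.

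**Inputs**
- Cycle length 4 weeks, tremelimumab in cycles 1–4 only (section 7.1.1). Cycle *k* is therefore dosed at week 4(*k* − 1), taking week 0 as the first dose.
- Treatment can stop after any number of durvalumab-alone doses (section 7.2).
- Periods of 6 months after the combination and 3 months after durvalumab alone (section 4.1.9).
- Assumptions: dosing on schedule; 6 months = 26 weeks and 3 months = 13 weeks.

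**Formula**

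Let *T* be the week of the last tremelimumab dose and *D* the week of the last durvalumab-alone dose.

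Gap = (*T* + 26) − (*D* + 13) = 13 − (*D* − *T*) weeks.

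For the *j*-th durvalumab-alone dose, *D* − *T* = 4*j*, so gap = 13 − 4*j*.

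**Four tremelimumab doses:** *T* = 4 × (4 − 1) = week 12; the 6-month period ends at week 12 + 26 = 38.

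| Last dose | *D* (week) | 3-month period ends | Gap to week 38 |
|---|---|---|---|
| Cycle 5 | 16 | 29 | 9 weeks early |
| Cycle 6 | 20 | 33 | 5 weeks early |
| Cycle 7 | 24 | 37 | 1 week early |
| Cycle 8 | 28 | 41 | none (3 weeks later) |

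A patient who stops after cycle 4 is covered to week 38. On the short reading, one who also takes cycle 5 is covered only to week 29.

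**Tremelimumab stopped earlier, durvalumab continued.** The gap depends only on *j*, so the same three values recur. After two tremelimumab doses, *T* = week 4 and the 6-month period ends at week 30. The 3-month period ends at weeks 21, 25, 29 and 33 for a last dose in cycles 3, 4, 5 and 6, giving gaps of 9, 5, 1 and none.

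**Sensitivity to the definition of a month.** With true calendar months, over a four-year run of dates for the last combination dose, the gaps are 61–65 days (*j* = 1), 33–37 days (*j* = 2) and 5–9 days (*j* = 3). At *j* = 4 the 3-month period ends 18–23 days after the 6-month one. A site that counts a month as 4 weeks would see 8, 4 and 0 weeks.

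**Is stopping in cycles 5–7 realistic?** Imaging is every 12 weeks (section 5.0). Under section 10.1, a clinically stable patient with unconfirmed progression at week 12 continues until a reassessment at least 4 and preferably no more than 8 weeks later. That is week 16 to 20, when cycles 5 and 6 are dosed. A patient who stops for progression at the week-24 scan would have a last dose in cycle 6 (week 20) or cycle 7 (week 24). The affected cycles are ordinary stopping points.

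**The case against.** The best reply is that each period is tied to its own dose, nothing says a later durvalumab dose cancels the earlier 6 months, and so the natural reading is to observe both. No text endorses the shorter reading, and nothing shows that a site has used it. That is fair, and it is why this is an ambiguity and not a mandated error. But the sentence offers the two periods as alternatives, and a site that picks the second has not departed from its words.

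Three safeguards might be thought to close the gap:

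- **Physician discussion.** Section 4.1.9 asks that stopping birth control be discussed with a physician, but only once the period has ended. It does not say when that is.
- **Time on study.** Contraception is also required while on study. Section 6.2 follows registered patients until death or until told otherwise, and Appendix IV continues survival contact every 3 months for 2 years. If that counts as being on study, the gap largely disappears. The term is undefined, however, and section 10.2 says patients with unequivocal progression "will stop all treatment and go off study at the time" it is documented. Patients who stop without progression are better placed, since section 10.4 keeps those with ongoing response or stable disease in 3-monthly follow-up unless they have started other systemic therapy.
- **Pregnancy reporting.** Section 9.3.2 would capture a pregnancy in the disputed weeks but would not prevent it.

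Three limits stand. The 9 weeks is a maximum, reached only with exactly one durvalumab-alone dose and the narrow readings of both phrases. The consent form was not available for review and may already be clear. The toxicity rules that would govern stopping tremelimumab early sit in a separate file cited in Appendix II.

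The male-patient sentence, as extracted, also attaches 3 months to the combination, twice. This may be a typing or PDF-reading slip. The finding does not rely on it, but it is another reason to replace the clause.

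**Conclusion.** The concern holds. For patients treated past the combination cycles, section 4.1.9 supplies two end dates and no rule for choosing between them, and nothing else in the protocol reliably supplies one. On the 3-month reading, contraception stops 9, 5 or 1 weeks inside the 6-month period for the first, second or third durvalumab-alone dose, and there is no shortfall from the fourth. These figures assume 4-weekly dosing on schedule and months of about 4.33 weeks; calendar months shift them by a few days.

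The number of patients exposed cannot be given. The documents report neither time on treatment nor how many patients have childbearing potential or such a partner. Response rate, sample size and every planned analysis are unaffected. This is a participant-safety wording fault that should be corrected because the correction is cheap.

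**What to change.** In the female-patient, male-patient/partner and sperm-donation sentences of section 4.1.9, replace the two-part clause with: *for 6 months after the last dose of tremelimumab or 3 months after the last dose of durvalumab, whichever is later*. This keeps both stated periods, leaves a patient who stops after cycle 4 at week 38, takes the cycle 5 patient from week 29 to week 38, and removes the garbled repetition in the male sentence. Align the consent form if it uses the same text.

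The cost is one phrase in three sentences. Visits, sample size and analysis do not change. The only burden is up to about 9 more weeks of contraception for patients who would otherwise have been advised on the shorter reading. If few patients remain in the affected window, a written clarification to sites could serve in the meantime.
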